23. The female subject is pregnant, lactating (breast feeding), or planning a pregnancy during the course of the study. Or, the female subject is of child-bearing potential and is not using a highly effective method(s) of birth control, including sexual abstinence. Or, the female subject is unwilling to continue using a highly effective method of birth control throughout the duration of the study.  
*Note:* A highly effective method of birth control is defined as one that results in a low failure rate (i.e., less than one percent per year) when used consistently and correctly, such as implants, injectables, combined oral contraceptives, some intrauterine devices (IUDs), sexual abstinence, or a vasectomized partner.

24. The subject has a history of active alcohol and/or drug abuse that, in the judgment of the Investigator, would impair the subject's ability to comply with the protocol.

25. The subject's health status would, in the judgment of the Investigator, be jeopardized by participating in the study.

26. The subject has used an investigational product within 3 months prior to REACT injection without receiving written consent from the Medical Monitor.

**Number of Sites:** Up to 10 clinical centers will be included in the study.

**Study Duration:** treatment to begin as soon as the REACT product is made available and assuming a one-month interval prior to receiving the first REACT injection, and assuming a 6-month interval before receiving the second injection, plus a 24 month follow up period after the final injection, the duration of treatment would be:

- 31 months for a series of 2 REACT injections

**Study Enrollment:** up to 10 subjects will be enrolled into the study. Patients who complete screening procedures satisfying all I/E criteria will be enrolled into the study immediately prior to the biopsy. Patients who do not meet all criteria before the biopsy is taken will be considered screen failures. Patients who have a biopsy but are not injected for whatever reason will be discontinued from the study and may be replaced. Once a patient has been injected, the patient will have completed treatment and every effort should be made to ensure the patient completes all follow-up visits.

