**Table 1: Time and Events Table**

Abbreviations: AE (adverse event); ConMeds (concomitant medications); DSMB (Data Safety and Monitoring Board); ECG (electrocardiogram); EOS (End-of-Study Visit); I /E (inclusion /exclusion); KDQOL (Kidney Disease Quality of Life Survey); MRI (magnetic resonance imaging); REACT (Renal Autologous Cell Therapy); PE (physical examination).

Notes:

- \* Day 1 follow-up visit should only be conducted if there is a safety event identified during or after the kidney biopsy.
- \*\* Every attempt should be made to ensure the second REACT injection is administered 6 months (+4 weeks) after the first injection. In the event that the subject cannot schedule his/her second REACT injection 6 months after receiving the first injection or cannot keep his/her scheduled 6-month visit, ProKidney and the Medical Monitor must be notified immediately. The expectation is that the subject and the clinical center will accommodate the Sponsor's preference that the series of 2 REACT injections should be administered no more than 6 months apart.
- a. If the screening assessment falls outside of the 60-day window before renal biopsy, re-screening will be performed as described in Screening ([Section 6.1](#)).
- b. Because the second REACT injection will occur 6 months (+4 weeks) after the first injection, the 6-month visit may not be scheduled.
- c. In the event that a second REACT injection will not be administered, the subject will undergo all follow-up assessments after the last REACT injection at the 24-month EOS Visit.
- d. The EOS Visit will take place 24 months after the last REACT injection, or when the subject is terminated from the study by the Investigator ([Section 8.6](#)) or when the subject voluntarily discontinues from the study ([Section 5.4](#)).
- e. The Informed Consent Form must be signed and dated prior to conducting any study-specific procedures, including those at the Screening Visit. Signing the Informed Consent Form starts the 60-day timeline for screening.
- f. The PE and interim PE are described in [Section 7.2.2](#).
- g. Vital signs include heart rate, resting blood pressure, respiration rate, and body temperature. ([Section 7.2.1](#)). At the Pre-Biopsy Visit (Day -3 to Day -1) and the Pre-Injection Visit (Day -14 to Day -10) three BP measurements will be taken and the average will be used to satisfy entry criteria.

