## 5. STUDY POPULATION

### 5.1. Subject Inclusion Criteria

Unless otherwise noted, subjects must satisfy each inclusion criterion to participate in the study. Inclusion criteria will be assessed at the Screening Visit, prior to renal biopsy, and before each REACT injection unless otherwise specified.

1. The subject is male or female, 30 to 65 years of age on the date of informed consent.
2. The subject has an established diagnosis of T2DM.
3. The subject has an established diagnosis of diabetic nephropathy as the underlying cause of renal disease.
4. The subject has an established diagnosis of CKD not requiring renal dialysis, defined as having an eGFR between 14 and 20 mL/min/1.73m^2 inclusive at the Screening Visit and prior to REACT injection.
5. The subject has blood pressure less than 150/90 at the Screening Visit, prior to renal biopsy, and prior to REACT injection(s). At the time of the biopsy and injections, the subject's BP should not be significantly below the previously recorded stable pressure.
6. The subject has stable blood pressure and is maintained on a stable anti-hypertensive medication regimen, if treatment for hypertension is necessary. If treatment includes an angiotensin-converting-enzyme inhibitor (ACEI) or an angiotensin receptor blocker (ARB), that treatment must have been initiated at least 8 weeks prior to renal biopsy. Treatment must be stable during the 6-week period immediately prior to REACT injection. Stable treatment is defined as dose adjustment to no less than one half of the current dosage or to no more than 2 times the current dosage. Dose interruptions up to 7 days due to medical necessity are allowed.
7. A minimum of 3 measurements of eGFR or sCr should be obtained at least 3 months apart prior to the Screening Visit or within the previous 24 months to define the rate of progression of CKD. The subject should have adequate, historical clinical data to provide a reasonable estimate of the rate of progression of CKD. The Medical Monitor may be consulted to ensure there is sufficient data.
8. The subject is willing and able to refrain from NSAID consumption (including aspirin) as well as clopidogrel, prasugrel, or other platelet inhibitors during the period beginning 7 days before through 7 days after both the renal biopsy and REACT injection(s).

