## 5.2. Subject Exclusion Criteria

Subjects who satisfy any exclusion criterion listed below are not eligible to participate in the study. Exclusion criteria will be assessed at the Screening Visit, before renal biopsy, and before each REACT injection unless otherwise noted.

1. The subject has a history of type 1 diabetes mellitus.
2. The subject has a history of renal transplantation.
3. The subject has a serum HbA1c level greater than 10% at the Screening Visit.
4. The subject has uncontrolled diabetes (defined as metabolically unstable by the Investigator).
5. The subject has hemoglobin levels less than 9 g/dL prior to each REACT injection.
6. The subject has abnormal coagulation status as measured by activated partial thromboplastin time (APTT), prothrombin time international normalized ratio (PT INR), and/or platelet count at the Screening Visit.
7. The subject has a bleeding disorder(s) or is taking anticoagulants, such as Coumadin® (warfarin) or direct thrombin inhibitors that, in the judgment of the Investigator, would interfere with the performance of study procedures.
8. The subject has small kidneys (average size less than 9 cm) or has only one kidney, as assessed by ultrasound and/or MRI prior to renal biopsy, unless earlier radiology reports (generated within 1 year of the Screening Visit) are made available to confirm kidney size and number.
9. The subject has a known allergy or contraindication(s), or has experienced severe systemic reaction(s) to kanamycin or structurally similar aminoglycoside antibiotic(s)
10. The subject has a history of anaphylactic or severe systemic reaction(s) or contraindication(s) to human blood products or materials of animal origin (e.g., bovine, porcine).
11. The subject is not a good candidate to undergo percutaneous REACT injection, in the judgment of the surgeon or physician who will perform the procedure. This includes individuals who are morbidly obese (defined as BMI greater than 45 kg/m^2), have excessive fat surrounding the kidney, or who are otherwise at excessive risk for serious complications.
12. The subject has a history of severe systemic reaction(s) or any contraindication to local anesthetics or sedatives.
13. The subject has a clinically significant infection requiring parenteral antibiotics within 6 weeks of REACT injection.
14. The subject has acute kidney injury or has experienced a rapid decline in renal function during the last 3 months prior to REACT injection.

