If continued eligibility cannot be verified for a particular subject, the site should contact ProKidney who will alert the manufacturing staff not to prepare the REACT product. The Investigator and ProKidney will discuss the reason(s) that the subject did not qualify and determine the best course of action. For example, if the subject was excluded for a temporary condition (e.g., active infection) then it may be possible to manufacture REACT at a later date, assuming future eligibility can be established. If the results of pre-treatment assessments indicate that it is highly unlikely for that subject to become eligible for REACT injection(s), then the subject should be discontinued from the study. If REACT injection is delayed (e.g., due to an intercurrent illness), the renal scintigraphy study, if conducted, does not need to be repeated prior to injection.

Eligible subjects will arrive at the hospital or clinical research center on the morning of REACT treatment. The subject will be injected with autologous REACT using a percutaneous approach as discussed in [Section 7.5.2](#).

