#### 6.5. Follow-up Visits

The subject will return to the clinic for follow-up visits on Days 1 (if discharged day of REACT injection), 7, 14, and 28 ( $\pm$  3 days) and Months 2, 3, 4 and 5 ( $\pm$  7 days) after the first REACT injection, and on Days 1 (if discharged day of REACT injection), 7, 14, and 28 ( $\pm$  3 days) and Months 2 and 3 ( $\pm$  7 days) after the second REACT injection ([Table 1](#) and [Table 2](#)). The subject will also report to the clinical center 10 to 14 days before the planned, final REACT injection to undergo pre-treatment assessments. **Every attempt should be made to ensure that the second REACT injection is administered 6 months after the first injection.**

Following the final REACT injection, subjects will complete long-term, follow-up assessments of safety and efficacy through Months 6, 9, 12, 15, 18, 21, and 24 ( $\pm$  7 days) post-treatment.

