### 8.6. Stopping Rules for an Individual Subject

The Investigator, Medical Monitor, DSMB, and Sponsor may remove any subject from the study for:

- Any clinical AE, laboratory abnormality, intercurrent illness, other medical condition or situation whereby continued participation in the study would not be in the best interest of the subject.
- Development of any exclusion criterion.

If a subject is terminated from the study, EOS assessments should be conducted at the last visit.

If any of the following events occur, no additional subjects can receive REACT injections until review by the DSMB has been completed:

- An SAE that is rated as severe or life-threatening and, in the judgment of the Investigator, is related to REACT or study procedures
- Death of an enrolled subject
- Similar SAE's in more than one subject that are related to REACT, in the judgment of the Investigator
- Inability to deliver a minimum of 50% of the dose of REACT in more than one subject due to surgical or other issues

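### Protocol Section 6.3 can be read as taking a once-injected subject off study when the second injection is ruled out, which conflicts with the synopsis and Table 1/2 note c and could cut about 18 of the 24 months of safety follow-up

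*Protocol*

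**What the plan says.** **Re-qualification applies to both injections.** Protocol Section 5.1 states: "Inclusion criteria will be assessed at the Screening Visit, prior to renal biopsy, and before each REACT injection unless otherwise specified". Section 5.2 states: "Exclusion criteria will be assessed at the Screening Visit, before renal biopsy, and before each REACT injection unless otherwise noted". Inclusion criterion 4 requires an eGFR of 14 to 20 mL/min/1.73m2 "inclusive at the Screening Visit and prior to REACT injection". Section 6.5 brings the subject back "10 to 14 days before the planned, final REACT injection to undergo pre-treatment assessments".

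**What follows a failure to re-qualify.** Section 6.3 has the investigator and the sponsor discuss the reason and agree what to do. Where the results make it "highly unlikely for that subject to become eligible for REACT injection(s), then the subject should be discontinued from the study", that is the outcome. The sentence has no restriction to subjects who have never been injected.

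**Removal for a new exclusion criterion.** Section 8.6 lets the investigator, Medical Monitor, DSMB or sponsor remove a subject from the study. One listed ground is "Development of any exclusion criterion".

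**Text pointing the other way.** The synopsis (Study Enrollment) discontinues patients who were biopsied but not injected. For a patient who has been injected it says "every effort should be made to ensure the patient completes all follow-up visits". Note c to Tables 1 and 2 says: "In the event that a second REACT injection will not be administered, the subject will undergo all follow-up assessments after the last REACT injection", and goes on to name the 24-month EOS Visit. The SAP appendices repeat note c.

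**The concern.** The primary endpoint is procedure- or product-related AEs through 24 months post-injection, in at most 10 subjects. A subject who has had one injection and then fails the second qualification check is one whose later course the study needs to see. If the site follows 6.3 as written, that subject leaves at the qualification visit. Under Section 5.4 a subject who leaves after injection cannot be replaced.

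Some reasons for failing re-qualification are themselves signs of worsening, such as an eGFR below 14 or the rapid decline in exclusion criterion 14. The loss can therefore be informative. The SAP does nothing to correct for it:

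- AE incidence is divided by all subjects in the analysis set, with no allowance for time observed (7.2.5).
- Missing data stay missing (4.5).
- Time to dialysis is censored at the last visit (6.3.5).

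**Working it through.** **1. The plan's own figure.** Protocol Section 4.5: 1 month to the first injection + 6 months between injections + 24 months of follow-up = 31 months. This agrees with the stated duration.

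**2. Can the 6.3 sentence reach an injected subject?** Sections 5.1, 5.2 and 6.5 place an eligibility check before the second injection, and the 6.3 sentence speaks of injections without saying which. Elsewhere the protocol does draw the line when it means to: the synopsis refers to patients biopsied but not injected, and the first bullet of Section 6.6 is confined to subjects between biopsy and injection. The 6.3 sentence has no such limit, so on its words it reaches a once-injected subject.

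**3. Follow-up lost by such a subject.** The second qualification visit falls at t = (6 × 30.4375 + w − p) / 30.4375 months after the first injection. Here w is 0 to 28 days (the +4-week window), p is 10 to 14 days before the planned injection, and 30.4375 days is the average month. The loss is 24 − t.

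| w (days) | p (days) | t (months) | Lost of 24 | Share |
|---|---|---|---|---|
| 0 | 14 | 5.54 | 18.46 | 76.9% |
| 0 | 10 | 5.67 | 18.33 | 76.4% |
| 28 | 14 | 6.46 | 17.54 | 73.1% |
| 28 | 10 | 6.59 | 17.41 | 72.5% |

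With 10 injected subjects the plan holds 10 × 24 = 240 person-months after the last injection. Each subject lost this way removes 17.41/240 to 18.46/240, or 7.3% to 7.7%.

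**4. How many subjects?** The documents give no expected decline, so this cannot be derived. To show the range, assume that eGFR at the first injection is uniform on 14 to 20 and falls by 2 to 8 mL/min/1.73m2 per year. By 5.6 months the fall is 2 × 5.6/12 = 0.93 to 8 × 5.6/12 = 3.73. The share below 14 is 0.93/6 = 15.6% to 3.73/6 = 62.2%, or about 1.6 to 6.2 of 10. This counts subjects below the eGFR floor. It does not count subjects who would actually be discontinued.

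**5. Effect on the AE summary (assumed values).** Suppose a true 24-month risk of 30% at constant hazard. The risk by 5.6 months is 1 − 0.70^(5.6/24) = 8.0%.

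- If 3 of 10 leave then, expected crude incidence on the full denominator is (7 × 30% + 3 × 8.0%)/10 = 23.4%.
- If 5 of 10 leave, it is 19.0%.
- For true risks of 10% to 50% with 3 leaving, it is 7.7% to 39.5%.

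Events concentrated soon after the procedure would make the shortfall smaller. A higher later risk in those who leave would make it larger.

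**6. If no event is seen.** The exact one-sided 95% upper limit is 1 − 0.05^(1/n): 25.9% with n = 10 followed to 24 months, 34.8% with n = 7, and 45.1% with n = 5.

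**The case against.** The strongest reply is that the text written for this situation already keeps the subject in the study. The synopsis separates injected from uninjected patients, and note c deals with the second injection not being given. Earlier in Section 6.3 itself, the response to renal deterioration, malignancy or infection is only to withhold the second injection. Section 8.1.1 requires AEs to be recorded through 24 months after the final injection, whether or not the subject stays eligible. SAP Section 4.9 defines periods for one-injection subjects running to withdrawal or completion. On that reading, the 6.3 sentence concerns subjects unlikely to qualify for any injection. This stands to the extent that a reader who infers that injected subjects will lose follow-up because they deteriorated goes further than the documents. It does not remove the contradiction, because the sentence is an instruction to sites and is not so limited.

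A reader might also infer that 8.6 forces removal whenever an exclusion criterion appears. It does not. The clause is permissive, and note d to Tables 1 and 2 provides an EOS Visit for such a termination. Several criteria are also tied to a time: 18 to Screening, and 5, 14 and 15 to the period before an injection.

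Nor would every loss reflect a poor course. Re-qualification can fail because eGFR is above 20, because of blood pressure, or because an investigational product was used.

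Finally, the losses would not be invisible. SAP Section 5.1 tabulates stage of and reason for withdrawal, Section 7.2.5 tabulates TEAEs leading to discontinuation, and Protocol Section 6.6 requires an EOS Visit and delays discontinuation while a related SAE is unsettled. These show that a subject left. They do not supply the follow-up after leaving.

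**Conclusion.** The point holds as a contradiction with consequences for the primary endpoint. Section 6.3, read literally, takes a once-injected subject off study about 5.5 to 6.6 months after the only injection. The synopsis and note c keep that subject in follow-up to 24 months. The size is firm per subject: about 17.4 to 18.5 of 24 months (73% to 77%). It rests only on the stated visit timing and on literal use of the sentence.

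The number of subjects affected is not in the documents, so the figures for the eGFR floor, crude incidence and zero-event limits are illustrations under stated assumptions. The supportable claim is that injected subjects can lose follow-up, that the loss can be related to deterioration, and that the SAP has no correction for it. Section 8.6 is a secondary matter of consistency.

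**What to change.** In Protocol Section 6.3, limit discontinuation from the study to subjects who have received no REACT injection. State that an injected subject who does not qualify for the second injection remains in scheduled follow-up to 24 months after the last injection, consistent with the synopsis and note c. While doing so, make clear that the interim visits in Section 6.5 apply, since note c can be read as placing all assessments at the 24-month visit.

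Reconcile Section 8.6 with the synopsis and note c, so that ineligibility for a further injection is kept distinct from leaving safety follow-up. Whether a further injection is given stays governed by the existing text.

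The cost is wording in two sections and a clarification of note c. If the Section 6.5 schedule is confirmed for one-injection subjects, no visit type is added. Separately, and not needed to resolve the contradiction, the AE tables could show time observed and the number of subjects followed to 24 months.

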#### 6.4. Discharge After REACT Injection

On the day after REACT injection and prior to discharge, an ultrasound will be performed to detect possible, subclinical adverse effects (e.g., swelling, fluid accumulation). If product- or procedure-related AE's occurred following REACT injection, the subject should not be discharged until the AE's have resolved, stabilized, or returned to baseline. If consistent with the site's standard practice, the subject may be discharged the same day as the REACT injection after no less than 2 hours of observation and monitoring.

#### 6.5. Follow-up Visits

The subject will return to the clinic for follow-up visits on Days 1 (if discharged day of REACT injection), 7, 14, and 28 ( $\pm$  3 days) and Months 2, 3, 4 and 5 ( $\pm$  7 days) after the first REACT injection, and on Days 1 (if discharged day of REACT injection), 7, 14, and 28 ( $\pm$  3 days) and Months 2 and 3 ( $\pm$  7 days) after the second REACT injection ([Table 1](#) and [Table 2](#)). The subject will also report to the clinical center 10 to 14 days before the planned, final REACT injection to undergo pre-treatment assessments. **Every attempt should be made to ensure that the second REACT injection is administered 6 months after the first injection.**

Following the final REACT injection, subjects will complete long-term, follow-up assessments of safety and efficacy through Months 6, 9, 12, 15, 18, 21, and 24 ( $\pm$  7 days) post-treatment.

#### 6.6. End-of-Study Visit

This section describes situations in which a subject will undergo the EOS visit; for example, due to premature discontinuation from the study or completion of all protocol-specified follow-up visits.

- If a subject discontinues from the study after undergoing the renal biopsy but before REACT injection, then that subject should complete all EOS assessments except for the MRI and/or renal scintigraphy studies. These imaging studies should only be completed if, in the judgment of the Investigator, one and/or the other would provide critical safety information needed for patient care. If the subject is experiencing an investigational product- or study procedure-related SAE, then the subject will not be discontinued until the SAE has resolved, stabilized, or returned to baseline.
- If a subject discontinues from the study after undergoing one or two REACT injections but before completing all of the protocol-specified follow-up visits, then he/she should have the EOS Visit at the time of discontinuation. For these subjects, the Investigator will determine whether or not it is clinically prudent to perform one or both of the imaging studies (i.e., MRI and renal scintigraphy). If the subject is experiencing an investigational product- or study procedure-related SAE, then the subject will not be discontinued until the SAE has resolved, stabilized, or returned to baseline.
- If a subject completes all of the protocol-specified follow-up visits, he/she will undergo all EOS assessments 24 months after the final REACT injection at the EOS Visit. If the subject is experiencing an investigational product- or study procedure-related SAE, then the subject will not be discontinued until the SAE has resolved, stabilized, or returned to baseline.

